8.2. Discussion of Trial Design

The initial 2x48-hour treatment period (Part 1) is double-blind and placebo controlled to avoid bias in the assessment of the effect of dasiglucagon on GIR. A crossover design has been chosen to limit the influence of inherent variability of the population, which allows for recruitment of fewer patients compared to a parallel-group design, reflecting the ultra-rare status of the disease. All patients will receive dasiglucagon in open-label Part 2. According to International Council for Harmonisation (ICH) guidelines, for the conduct of clinical trials in rare diseases, where the anticipated likelihood of considerable benefit is high, such design has some potential efficiencies because all patients will be exposed to test drug, which is of particular importance in rare diseases.¹⁶

8.3. Trial Sites

The trial will take place at 5 to 7 sites in the US and Europe that are experienced in the treatment of CHI. A total of 12 patients with CHI is planned to be randomized and exposed to the trial product. Patients who withdraw prematurely will not be replaced.

8.4. Point of Contact

A point of contact will be identified to provide information to each patient's parent(s)/guardian about where to obtain information on the trial, the patient's rights, and whom to contact in case of trial-related injury. This information will be provided in the patient information and informed consent form (ICF).

9. PATIENT POPULATION

9.1. Selection of Trial Population

A screening log of potential trial candidates must be maintained at each trial site.

9.2. Trial Entry Criteria

9.2.1. Inclusion Criteria

A patient will be eligible for trial participation if he or she meets all of the following criteria:

1. CHI diagnosis established based on the following:
 - a. Hyperinsulinemia: plasma insulin above the limit of detection of the assay documented during an event of hypoglycemia, and/or
 - b. Hypofattyacidemia: plasma free fatty acid <1.7 mmol/L, and/or
 - c. Hypoketonemia: Beta-hydroxybutyrate <1.8 mmol/L, and/or
 - d. Glycemic response: an increase in PG of >30 mg/dL (1.7 mmol/L) after 1 mg IV or IM glucagon administration
2. Male or female, age ≥ 7 days and <12 months at screening
3. Body weight of ≥ 2.0 kg (4.4 lbs.)
4. Continuous IV glucose requirement to prevent hypoglycemia
5. One or both parents* or guardians of the patient must provide signed informed consent before any trial related activity is performed. (*according to local regulations)

9.2.2. Exclusion Criteria

A patient will be excluded from the trial if he or she meets any of the following criteria:

1. Is suspected of having a transient form of CHI (e.g., transient hyperinsulinism due to maternal diabetes or perinatal stress)
2. Was born preterm below 34 weeks of gestational age
3. Presence of hypertension or hypotension, including circulatory instability requiring supportive medication or presence of pheochromocytoma
4. Known or suspected presence of severe brain damage
5. Evidence of metabolic, endocrine, or syndromic causes of hypoglycemia not due to hyperinsulinism
6. Use of systemic corticosteroids, e.g., hydrocortisone >20 mg/m² body surface area or equivalent within 5 days before screening

7. Prior use of lanreotide, sirolimus (mechanistic target of rapamycin [mTOR inhibitors]), anti-inflammatory biological agents, or other immune-modulating agents. Prior use of octreotide is allowed after a minimum of 48-hour washout before randomization.
8. Aspartate aminotransferase (AST) or alanine aminotransferase (ALT) >2.5 X the upper limit of normal (ULN), or estimated glomerular filtration rate (eGFR) <30 mL/min/1.73m² adjusted by a pediatric formula (e.g., Schwartz formula)
9. Any clinically significant abnormality identified on echocardiogram that in the opinion of the investigator would affect the subject's ability to participate in the trial
10. Known history of laboratory test results obtained before screening that show presence of HIV, hepatitis B surface antigen, hepatitis C antibody, or hepatitis A immunoglobulin M
11. Any recognized clotting or bleeding disorder
12. Previous administration of dasiglucagon (previously referred to as ZP4207)
13. Known or suspected allergy to the trial drug or related products
14. Previous participation (randomization) in the clinical program (Trials ZP4207-17103 or -17109)
15. Has participated in an interventional clinical trial (investigational or marketed product) within 30 days of screening, or plans to participate in another clinical trial, except for 18F-Dopa PET CT/MRI investigation (where performed as a part of a research trial), which is allowed for diagnosis of focal CHI.
16. The use of prescription or non-prescription medications known to cause QT prolongation.

9.2.3. Randomization Exclusion Criteria

A screened patient will not be randomized if:

1. Mean IV glucose requirement is <10 mg/kg/min to maintain glycemia above 70 mg/dL (3.9 mmol/L) during the previous 24 hours prior to randomization
2. Use of glucagon within 24 hours before randomization.
3. Use of additional enteral glucose within 24 hours before randomization. Patients should be transitioned to IV glucose infusions only at least 24 hours before randomization.
4. Is not sufficiently clinically stable on IV GIR only (\pm diazoxide, as applicable), in the opinion of the investigator, to undergo the placebo-controlled randomized Part 1 of the trial (2x48 hours).

The Randomization Visit may be rescheduled once if Randomization Exclusion Criterion 2 is met.

9.3. Premature Patient Withdrawal

Randomization day exclusion criteria are described in Section 9.2.3.

Patients' parent(s)/guardian will be advised that they are free to withdraw their child from participation in this trial at any time, for any reason, and without prejudice. Every reasonable attempt should be made by the investigator to keep patients in the trial to obtain data for the primary endpoint in Part 1 and for safety follow-up even if trial treatment has been discontinued. However, patients must be withdrawn from the trial if their parent(s)/guardian withdraw consent to participate.

Investigators must attempt to contact patients' parent(s)/guardian who fail to attend scheduled visits by telephone or other means to exclude the possibility of an AE being the cause of withdrawal. Attempts to contact the patient must be documented. At least 3 phone calls and 3 written attempts to contact the patient will be made prior to considering them lost to follow-up. Should an AE be the cause of withdrawal, it must be documented, reported, and followed up as described in Section 12.3.

If a patient/parent(s)/guardian withdraws consent, the reason for withdrawal and the date of withdrawal will be recorded on the appropriate page of the electronic case report form (eCRF). Whenever possible and reasonable, the evaluations that were to be conducted at the completion of the trial should be performed at the time of premature withdrawal.

9.4. Treatment Discontinuation

To prevent missing data, patients should, to the extent possible, be kept in the trial; therefore, treatment discontinuation is often the preferred option in case of, e.g., substantial noncompliance with trial procedures or initiation of prohibited treatment that interferes with the efficacy and safety evaluation. If it is an investigator's decision to discontinue the patient's treatment, the investigator should, whenever possible, discuss the potential discontinuation of the treatment with the medical monitor. If the patient is discontinued from trial treatment by the investigator or by parent/guardian's decision, the reason for treatment discontinuation and the date of treatment discontinuation will be recorded on the appropriate page of the eCRF. The patient should be asked to continue in the trial by following the planned visit schedule and to have trial assessments performed according to the Schedule of Events. This is especially important during Part 1 of the trial where the primary endpoint is evaluated. As a minimum, the patient will be asked to attend the Follow-up Visit 28 days (\pm 3 days) after discontinuation of trial treatment.

9.5. Rescue Criteria

During Part 1, the IV glucose concentration and rate of infusion can be increased to avoid hypoglycemia. When the maximum (or maximum tolerable) dose of trial drug has been reached and the necessary amount of GIR to prevent hypoglycemia is likely to cause (in the investigator's opinion) a moderate or severe AE (e.g., volume overload), oral/gastric non-nutritional carbohydrates can be introduced to ensure the patient's safety whilst maintaining the maximum tolerable concentration and infusion rate of IV glucose.

During Part 2, patients are allowed to initiate and titrate oral/gastric non-nutritional carbohydrates, and initiate any CHI treatment.

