TRIAL DESIGN	
This is a combined phase 2 and 3, randomized, multinational trial to evaluate the efficacy and safety of individually titrated dasiglucagon in children \geq 7 days and $<$ 1 year of age who have been diagnosed with CHI, comprising 2 parts, a crossover (2 periods, 48 hours each), double-blind, placebo-controlled Part 1, and an open-label, single-arm Part 2 of 21 days.
 
After screening, eligible patients will complete a minimum 24-hour run-in period to confirm the IV glucose randomization requirement (\geq 10 mg/kg/min). All non-nutritional carbohydrates and carbohydrate fortification of feeds are prohibited during this 24-hour run-in period. After the run-in period, patients will be randomly assigned in a double-blind fashion to receive dasiglucagon or placebo for 48 hours, after which they will be crossed over to the other trial treatment for an additional 48 hours. At the time of crossover, the trial drug will be initiated from the starting dose of 10 μg/hr, and IV glucose infusion rate (GIR) will be set to the rate obtained at the end of the run-in period and titrated accordingly.
 
There will be no washout between the 2 periods in Part 1 to limit the length of time in which patients are reliant on IV GIR as their only means of preventing/treating hypoglycemia. This is deemed acceptable because:
 
• The half-life ($t_{1/2}$) of dasiglucagon is short (~30 minutes for the 0.6 mg dose and potentially shorter for lower doses, ~22 minutes) relative to the 48-hour duration of each crossover period. Moreover, for the primary endpoint, only the last 12 hours of the 48-hour period will be used for endpoint assessment.• Assuming a positive effect of dasiglucagon, the absence of washout is more conservative with respect to key secondary endpoints since a potential carry over effect of dasiglucagon in Period 2 is attributed to placebo. 
During Part 1, the trial drug and IV GIR should be adjusted according to the protocol-specified algorithm. Non-nutritional carbohydrates and/or carbohydrate fortification of feeds during Part 1 is only allowed when the maximum tolerable volume and concentration of IV glucose for the patient is reached, and should be limited to the minimum needed to ensure the patient's safety. All feedings (administered as parenteral nutrition, by nasogastric [NG] tube, gastrostomy, or normal route), will be recorded during this period. Safety assessments will be performed daily after initiation of the trial drug (active or placebo).

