During Part 1, the trial drug and IV GIR should be adjusted according to the protocol-specified algorithm (see Section 10.2). Non-nutritional carbohydrates and/or carbohydrate fortification of feeds during Part 1 is only allowed if the maximum tolerable volume and concentration of IV glucose for the patient is reached, and should be limited to the minimum needed to ensure the patient's safety (Section 9.5). All feedings (administered as parenteral nutrition, by NG tube, gastrostomy, or normal route), will be recorded during this period. Safety assessments will be performed daily after initiation of the trial drug (active or placebo).

After Part 1, patients will continue in open-label Part 2 to receive dasiglucagon for 21 days. Additional CHI treatments can be introduced during Part 2 if needed, if up-titration of dasiglucagon is not possible due to undesirable side effects or if the maximum dose level (70 µg/hr) has been reached. Gradual transfer from IV glucose to oral and gastric carbohydrates should be initiated in Part 2, enabling weaning of IV glucose and hospital discharge. Patients will continue to be hospitalized until IV GIR is weaned off; however, as soon as local site criteria for discharge are met, patients can be discharged to continue the treatment period at home. Visits are planned on Day 11 and Day 18 in Part 2. These visits can be converted to telephone visits if appropriate, at the investigator's discretion. On Day 25, the End of Treatment Visit will take place, and based on the investigator's confirmation of continued positive benefit-risk balance, patients will be offered the opportunity to enter the long-term extension trial (Trial ZP4207-17106) to continue dasiglucagon treatment. Patients who do not enter the long-term extension trial will have a Follow-up Visit 28 days after their last dose of trial drug.

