10.2. Treatments Administered

As long as the patient is receiving IV glucose, the PG will be measured and reviewed hourly using a hand-held PG meter. The IV GIR will be titrated to achieve glycemia of at least 70 mg/dL (3.9 mmol/L) (a minimum GIR will be established as the rate up-titrated after the patient drops at least once below 70 mg/dL [3.9 mmol/L]). When the patient is no longer on IV GIR, the PG will be checked according to local practice, but at least 3 times daily. The PG will be measured using the same trial-supplied hand-held PG meter during the entire trial.

Additionally, blinded CGM will be started 24 hours prior to randomization and continued until the end of Part 2.

Dosing of dasiglucagon will approximate continuous infusion by delivering small doses at frequent intervals via the infusion pump. The adjustment of trial drug dosing is closely linked to the PG level achieved, which in turn will govern the IV GIR. In Part 1 the algorithm in [Table 1](#) should be used.

The pump administers 0.000025 mL/dose ~ 0.1 µg/dose (4 mg/mL formulation):

- 10 µg/hr ~ 0.5 µg every 3 min
- 20 µg/hr ~ 1 µg every 3 min
- 30 µg/hr ~ 1.5 µg every 3 min
- 40 µg/hr ~ 2 µg every 3 min
- 50 µg/hr ~ 2.5 µg every 3 min
- 60 µg/hr ~ 3 µg every 3 min
- 70 µg/hr ~ 3.5 µg every 3 min

Table 1 Algorithm to Maintain Plasma Glucose

Plasma Glucose (mg/dL)	Plasma Glucose (mmol/L)	Action
<50	<2.8	Give 200 mg/kg of dextrose as a bolus and increase IV GIR by 2 mg/kg/min
50-59	2.8-3.3	Increase IV GIR by 2 mg/kg/min
60-69	3.3-3.9	Increase IV GIR by 1 mg/kg/min
70-80	3.9-4.4	No change
81-90	4.4-5.0	Reduce IV GIR by 0.5 mg/kg/min
91-100	5.0-5.5	Reduce IV GIR by 1 mg/kg/min
101-120	5.5-6.7	Reduce IV GIR by 1.5 mg/kg/min
>120	>6.7	Reduce IV GIR by 2 mg/kg/min

Abbreviations: GIR = glucose infusion rate; IV = intravenous

The IV GIR will be reviewed, evaluated, and adjusted (if indicated) every hour according to the above PG-driven algorithm to maintain a PG of >70 mg/dL (>3.9 mmol/L). Rechecks of PG are allowed.

Part 1 (Crossover, double-blind, randomized, placebo-controlled)

The starting dose of trial drug is 10 µg/hr at t=0. Every 2 hours (t=2, 4, 6, etc.), the dose will be increased by an additional 10 µg/hr until either:

- The patient is totally weaned off IV glucose, or
- Plasma glucose during the last 2 hours was constantly above 120 mg/dL (6.7 mmol/L), or

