- IV GIR has not decreased despite 2 sequential dose increments of trial drug (in this situation, the dose of trial drug should be maintained until the IV GIR can be further decreased or until crossover or the end of Part 1), or
- The maximum dose of 70 µg/hr is reached, or
- AEs emerge that are considered to be related to dasiglucagon (e.g., nausea/change in feeding pattern or increased vomiting) that are limiting further dose escalation

The 2-hour dose-adjustment interval will allow drug plasma levels to approach steady-state before the dose is further increased. The cumulative dose will not exceed 1.26 mg over the first 24 hours and 1.68 mg for each of the subsequent 24-hour periods.

At the time of crossover from the first 48-hour period to the second 48-hour period, the trial drug will again be titrated from the starting dose of 10 µg/hr, and IV GIR will be set to the rate obtained at the end of the run-in period and titrated accordingly.

Part 2 (Open label)

After Part 1, patients will continue in open-label Part 2 to receive dasiglucagon for a further 21 days. Since treatment allocation during Part 1 remains blinded, all patients are required to initiate dasiglucagon dosing at 10 µg/hr in Part 2, while IV GIR should be started at the rate obtained at the end of the run-in period.

During Part 2, the dasiglucagon dose, the amount and route of administration of carbohydrates (IV GIR, parenteral nutrition, gastric carbohydrate infusions, and carbohydrates from oral feeds) can be adjusted at the discretion of the investigator. The PG should be monitored at least hourly to adjust the IV GIR as appropriate and to avoid hypoglycemia. Additional concomitant medications, including somatostatin analogs and/or sirolimus/mTOR inhibitors, may be introduced at the investigator's discretion if the maximum dose level of dasiglucagon (70 µg/hr) has been reached or if further up-titration is not possible due to undesirable side effects.

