Fluid balance assessments are to be performed and documented at least every 8 hours as long as the patient is hospitalized and receiving IV glucose. These assessments will include administered IV and oral fluids, fluid loss from stools and urine by weighing of diapers, and vital signs of fluid balance status. Furthermore, daily body weight will also be part of the individualized assessment based on the patients overall status, at investigator's discretion. According to Section 9.5, the investigator should evaluate whether the IV glucose concentration should be increased to avoid volume overload or whether oral/gastric non-nutritional carbohydrates are to be introduced to ensure the patient's safety whilst maintaining the maximum tolerable concentration and infusion rate of IV glucose.

All details on IV GIR (including any bolus given) will be recorded in the eCRF.

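### Section 9.5 ties Part 1 carbohydrate rescue to a trial-drug dose not reached by infants held for non-response or still titrating; Section 8.1, the synopsis and the SAP state only an IV glucose limit

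*Protocol*

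**What the plan says.** The rule on rescue carbohydrate in Part 1 appears in several places. The wording is essentially the same in both current protocol versions (14.0 for Germany, 13.0 elsewhere).

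- **Protocol 9.5, Rescue Criteria**, sets two joint conditions. The first concerns the trial drug and the second the IV glucose: "When the maximum (or maximum tolerable) dose of trial drug has been reached and the necessary amount of GIR to prevent hypoglycemia" has to be, in the investigator's opinion, likely to produce a moderate or severe adverse event such as volume overload.
- **Protocol 8.1** says that such carbohydrate "is only allowed if the maximum tolerable volume and concentration of IV glucose for the patient is reached". It names no trial-drug dose and refers the reader to 9.5.
- **The synopsis** has the same single condition ("is only allowed when the maximum tolerable volume and concentration of IV glucose for the patient is reached"), and **SAP Section 3** repeats it. Neither mentions trial-drug dose.
- **Protocol 11.2.3.2** (fluid balance) cites 9.5 and asks the investigator to evaluate "whether oral/gastric non-nutritional carbohydrates are to be introduced". It sets no condition of its own.

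Protocol 10.2 decides who can meet the dose condition. "The starting dose of trial drug is 10 µg/hr at t=0", and every 2 hours "the dose will be increased by an additional 10 µg/hr until either" one of several stops applies. One stop is that "IV GIR has not decreased despite 2 sequential dose increments of trial drug (in this situation, the dose of trial drug should be maintained" until GIR can be lowered further, crossover, or the end of Part 1. Reaching 70 µg/hr and escalation-limiting related adverse events are separate stops in the same list.

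**The concern.** The dose condition in 9.5 depends on how far titration has gone, and 10.2 deliberately stops titration early in an infant who is not responding. An infant in that position who also reaches the limit of tolerable IV glucose satisfies the condition in 8.1, the synopsis and the SAP, but not the one in 9.5. The same is true of an infant who reaches the IV limit while still being titrated.

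Three things are at stake. The first is that a site facing this infant has no single instruction. The second is the primary endpoint, which counts IV glucose infusion only (SAP 6.1.7). A site that introduces enteral carbohydrate at the IV limit and a site that does not could record different GIR for the same clinical state, and the treatment-policy estimand takes GIR as reported. The third is the per-protocol set, which excludes major deviations. Whether a given rescue is compliant or a deviation depends on the section being read.

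**Working it through.** **Inputs (Protocol 10.2).** Start at 10 µg/hr; add 10 µg/hr every 2 h; maximum 70 µg/hr; hold after 2 sequential increments without a fall in GIR; cumulative dose at most 1.26 mg in the first 24 h and 1.68 mg in each later 24 h.

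**1. Reproduce the plan's caps.** Uninterrupted titration gives 10, 20, 30, 40, 50 and 60 µg/hr for 2 h each, then 70 µg/hr from 12 h.
- First 24 h: 2 × (10+20+30+40+50+60) + 12 × 70 = 420 + 840 = 1,260 µg = 1.26 mg.
- Next 24 h: 24 × 70 = 1,680 µg = 1.68 mg.

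Both match, so the schedule is read as intended. The maximum is reached no earlier than 12 h into each 48-hour period.

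**2. Apply the hold rule to an infant whose GIR never falls.** The dose is 10 at 0 h, 20 at 2 h (first increment) and 30 at 4 h (second increment). The step due at 6 h is not taken.
- Held dose: 30/70 = 43% of the maximum.
- First 24 h: 2×10 + 2×20 + 20×30 = 660 µg, against 1,260 µg.

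If GIR never falls and there is no intolerance, the dose condition is unmet for the whole 48 h.

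**3. Set the conditions side by side** for an infant at the IV glucose limit, taking the second 9.5 condition (likely adverse event) as met.

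| State of titration | IV limit (8.1, synopsis, SAP) | Dose condition (9.5) |
|---|---|---|
| At 70 µg/hr | met | met |
| Escalation stopped by a related adverse event | met | met |
| Held at 30 µg/hr, no fall in GIR | met | not met |
| Before 12 h, still titrating, no intolerance | met | not met |

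A hold for non-response cannot be counted as the maximum tolerable dose. Section 10.2 lists it apart from the adverse-event stop, and Section 10.7 likewise separates undesirable effects from absence of further effect.

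**4. How often might a hold occur?** The documents give no figure. As an assumption, let q be the chance that GIR falls in any 2-hour step, independently across the five steps that follow the first five increments. A patient escapes a hold if no two consecutive steps fail:

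P(no hold) = q⁵ + 5q⁴(1−q) + 6q³(1−q)² + q²(1−q)³.

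The chance of at least one hold is 100% at q = 0, 91% at 0.25, 59% at 0.5 and 20% at 0.75. The range is too wide to support a frequency, and a hold ends once GIR can be lowered.

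**5. Possible effect on the primary endpoint.** As an assumption, suppose enteral carbohydrate replaces 2 to 4 mg/kg/min of IV glucose throughout hours 36 to 48 of one period in one infant. The mean difference over 12 patients then moves by 2/12 = 0.17 to 4/12 = 0.33 mg/kg/min. That is 2% to 4% of the planned 7.5 mg/kg/min.

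**The case against.** The best reply is that 8.1 states a necessary condition, not a grant of permission, and cites 9.5 in the same sentence. On that view 8.1, the synopsis and the SAP summarise, 9.5 gives the detail, and nothing conflicts. Section 9.5 also says when carbohydrate can be introduced and contains no express prohibition. Both points are fair, and they mean that any bar is by implication. They do not close the gap. If the conditions stack, the held or still-titrating infant at the IV limit has no stated carbohydrate route, and no passage says that this is intended.

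A reader might go further and infer that 9.5 denies mainly placebo infants their only alternative to more IV glucose, and that both tested endpoints suffer. The documents do not support this:

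- Holds may well be more common on placebo, but no frequency is given. Table 1 lowers GIR at an hourly glucose of 81 mg/dL or more, so GIR can also fall on placebo. Infants not stable enough on IV glucose for Part 1 are not randomized (9.2.3).
- Other measures remain: a higher IV glucose rate or concentration (9.5), the Table 1 dextrose bolus, and marketed glucagon for severe hypoglycemia (10.11.2).
- The key secondary endpoint is total grams by any route over each 48-hour period, expressed per day. Route, and timing within the period, do not move it; it changes only if total grams change.
- The first 12 h of titration lie outside the last-12-hour window of the primary endpoint.

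**Conclusion.** The inconsistency is real, is present in both protocol versions, and follows from the text and the titration arithmetic alone. Absent intolerance, an infant held at 30 µg/hr for non-response, or any infant in the first 12 h of a period, does not meet the dose condition in 9.5 even when the IV glucose limit has been reached. The passages either conflict or jointly leave that infant without the carbohydrate route.

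The weight of the point lies in unclear rescue instructions for infants and in possible differences between sites. It does not rest on power. The frequency and the treatment imbalance are unknown. The effect on the primary comparison is also unknown and probably small; the 0.17 to 0.33 mg/kg/min per affected infant rests on an assumed substitution that persists through hours 36 to 48. Because the ambiguity concerns rescue and is cheap to remove, it should be corrected.

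**What to change.** Reconcile the synopsis and Sections 8.1, 9.5, 10.2 and 11.2.3.2 in both protocol versions, together with SAP Section 3, so that one set of conditions governs carbohydrate rescue in Part 1. State explicitly whether it covers (a) a patient whose trial-drug dose is held because GIR has not fallen and (b) a patient still being titrated. The clinical team decides which condition applies.

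Record the reason at each rescue start in the eCRF. Infusion details, IV GIR and carbohydrate by route are already collected, so this is one added field. For any rescue that has already taken place, settle its deviation status, and hence per-protocol membership, at the blinded data review.

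The cost is an amendment or clarification letter, a matching SAP sentence and one eCRF item. No extra patients or procedures are needed.

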10.11.1. Permitted Therapies

Regarding diazoxide, patients entering the trial either:

- Have tried diazoxide, but discontinued due to lack of efficacy. Minimum of 6 days' washout is required prior to randomization.
- Have tried diazoxide, but discontinued due to adverse events, or family choice, even if efficacy was established. Minimum of 6 days' washout is required prior to randomization.
- Have initiated diazoxide prior to screening, and continue on the treatment. Diazoxide dose should remain stable during Part 1 of the trial. Diazoxide should not be initiated during screening.
- Have never tried diazoxide. Diazoxide should not be initiated during screening or Part 1 of the trial.

Prior use of octreotide is allowed after a minimum 48-hour washout prior to randomization. Washout is required to eliminate the effect of octreotide during Part 1, where adjustment of GIR has to follow the protocol-defined PG-driven algorithm ([Table 1](#)) and the primary endpoint on mean GIR is assessed.

Somatostatin analogs and/or diazoxide can be introduced during Part 2 if needed, at the investigator's discretion, when the maximal limit of dasiglucagon (70 µg/hr) has been reached or if further up-titration is not possible due to undesirable side effects.

Addition of other CHI-specific treatments (e.g., sirolimus/mTOR inhibitors) during Part 2 need to be discussed with the medical monitor.

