10.11.2. Prohibited Therapies

The following therapies are prohibited:

During the entire trial:

- Systemic corticosteroids, e.g., hydrocortisone >20 mg/m² body surface area or equivalent within 5 days before screening.
- Anti-inflammatory biological agents or other immune-modulating agents.

- Other investigational agents.
- Marketed glucagon products within the last 24 hours prior to randomization and throughout the trial unless necessary for rescue therapy in case of severe hypoglycemia, as per local standard of care.
- Prescription or non-prescription medications known to cause QT prolongation.

During Screening and Part 1:

- Somatostatin analogs and sirolimus (mTOR inhibitors). No new CHI treatment is to be initiated during screening and Part 1. Octreotide is allowed in the screening period if discontinued at least 48 hours before randomization.

During Part 2 and follow-up:

- Initiation of somatostatin analogs, diazoxide and sirolimus (mTOR inhibitors) unless the maximum dose level of dasiglucagon (70 µg/hr) has been reached or further dasiglucagon up-titration is not possible due to undesirable side effects.

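### Protocol 9.5 lets any CHI treatment be started in Part 2 without condition, while 10.11.2 prohibits starting the main ones until a dose or tolerability condition is met

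*Protocol*

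**What the plan says.** Section 9.5 (Rescue Criteria) closes with its only statement on Part 2: "During Part 2, patients are allowed to initiate and titrate oral/gastric non-nutritional carbohydrates, and initiate any CHI treatment". It gives no dose or tolerability condition and no cross-reference.

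Section 10.11.2 (Prohibited Therapies) lists as prohibited, for Part 2 and follow-up: "Initiation of somatostatin analogs, diazoxide and sirolimus (mTOR inhibitors) unless the maximum dose level of dasiglucagon" of 70 µg/hr has been reached, or side effects rule out going higher.

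The same condition appears elsewhere:
- Section 8.1: "Additional CHI treatments can be introduced during Part 2 if needed, if up-titration of dasiglucagon is not possible due to undesirable side effects". Its alternative ground is having reached the top dose level. The Trial Design entry of the synopsis and SAP Section 3 match it.
- Section 10.2: "Additional concomitant medications, including somatostatin analogs and/or sirolimus/mTOR inhibitors, may be introduced at the investigator's discretion if the maximum dose level of dasiglucagon" has been reached or up-titration is not possible. The Treatment Regimens entry of the synopsis and SAP Section 3.4 match it.
- Section 10.11.1, for two of the drug classes: "Somatostatin analogs and/or diazoxide can be introduced during Part 2 if needed, at the investigator's discretion, when the maximal limit of dasiglucagon" has been reached, or up-titration is not possible.

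Section 10.11.1 adds a procedural step that 10.2 lacks: "Addition of other CHI-specific treatments (e.g., sirolimus/mTOR inhibitors) during Part 2 need to be discussed with the medical monitor".

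Protocol versions 14.0 (Germany) and 13.0 (all other countries) carry these provisions in the same terms, so this is current text in both.

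**The concern.** A rule on when other active drugs may be added should give one answer for a given patient. Here the rescue section and the prohibited-therapy section give opposite answers for a patient who has not met the condition.

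Three things hang on the answer:
- **Treatment.** Section 9.4 names the start of a prohibited treatment that interferes with evaluation as an example of when stopping trial drug, while keeping the patient in the trial, is often preferred. Whether that example applies depends on which section is read.
- **Analysis sets.** The per-protocol set excludes patients with major protocol deviations (Protocol 13.3, SAP Section 5). Neither document defines major or limits it to Part 1.
- **Part 2 summaries.** Weaning off IV glucose, discharge, hypoglycemia, carbohydrate amounts and CGM measures can all move when another CHI drug is added. Sites following different sections would add drugs at different points.

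**Working it through.** The main check is textual. The provisions side by side:

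| Place | Treatments covered | Condition | Medical-monitor discussion |
|---|---|---|---|
| 9.5 | any CHI treatment | none | none |
| 10.11.2 | somatostatin analogs, diazoxide, sirolimus | maximum level reached, or side effects prevent up-titration | none |
| 10.11.1 | somatostatin analogs, diazoxide | same | none |
| 10.11.1 | other CHI-specific drugs, e.g. sirolimus | not restated in that sentence | yes |
| 10.2, synopsis, SAP 3.4 | additional drugs, including somatostatin analogs and sirolimus | same | none |
| 8.1, synopsis, SAP 3 | additional CHI treatments | same | none |

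Three test cases show where the provisions part:

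1. *Below 70 µg/hr, no limiting side effects, somatostatin analog or diazoxide started in Part 2.* Permitted by 9.5, prohibited by 10.11.2, and outside the permission in 8.1 and 10.11.1. No reading satisfies all sections. This is the contradiction.
2. *At 70 µg/hr, somatostatin analog or diazoxide started.* No section forbids it. (Section 10.2 does not name diazoxide, but its list is inclusive.) No conflict.
3. *At 70 µg/hr, sirolimus started without contacting the medical monitor.* Consistent with 9.5, 10.2 and 10.11.2, but it misses the step in 10.11.1. A site that discusses first and then decides satisfies all four sections. This is a step missing from 10.2, not two incompatible rules.

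The dispute is therefore confined to starts made before the condition is met, plus the procedural gap for sirolimus.

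**Reach into Part 1.** Section 10.11.2 bars new CHI treatment during screening and Part 1, and the primary and key secondary endpoints are measured there. The plan's power figure uses n = 12, mean difference 7.5 and SD of differences 7.36 mg/kg/min (Protocol 13.2), with two-sided alpha 0.05 (Protocol 13.4). The noncentrality is (7.5 / 7.36) × √12 = 1.019 × 3.464 = 3.53. The noncentral t distribution gives power 0.894 with 11 degrees of freedom and 0.888 with 10, if one is spent on the period effect. Both agree with the stated 89%, and no input depends on Part 2 drug rules.

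**The one route back to Part 1 data.** A Part 2 event classed as a major deviation would remove the patient from the supportive per-protocol analysis. With 12 patients, one exclusion is 1/12 = 8%. The full-analysis-set results would not change.

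**The case against.** The strongest reply is that 9.5 is a single loose sentence. The condition stands in the synopsis, 8.1, 10.2, 10.11.1, 10.11.2 and the SAP, and 10.11.2 is the section dedicated to prohibited drugs, so a careful site would follow it. This stands to the extent that 9.5 is an outlier and the protocol is not evenly split. It does not remove the conflict. The Part 1 paragraph of 9.5 does state a dose condition, so its absence from the Part 2 sentence below can be read as deliberate, and no order of precedence is given.

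It is also fair that Part 2 is open-label, single-arm and descriptive. Dasiglucagon dose and carbohydrate route are already at the investigator's discretion, and concomitant drugs are recorded and summarized by part. A reader might infer that the contradiction makes Part 2 uninterpretable as one regimen. The documents do not support that: Part 2 was never a fixed regimen, and every reading allows some add-on treatment.

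Two further inferences are tempting:
- **Sirolimus banned throughout.** Section 10.11.2 prohibits for the whole trial "Anti-inflammatory biological agents or other immune-modulating agents", and exclusion criterion 7 lists sirolimus next to similar words. But 10.11.2 has its own sirolimus clauses for Part 1 and Part 2, which would be pointless if the general ban covered it. Exclusion 7 lists sirolimus as a separate item and concerns prior use.
- **Several competing policies.** The table can look like three or more rules. It reduces to one conditional rule, one unconditional sentence and one missing procedural step.

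**Conclusion.** The point holds in limited form. Sections 9.5 and 10.11.2 contradict each other, in both current protocol versions, for CHI drugs started in Part 2 before the dose or tolerability condition is met. For those starts, deviation status and what follows from it cannot be decided from the text. Other Part 2 deviations can still be judged. The sirolimus mismatch between 10.2 and 10.11.1 is procedural and smaller.

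The effect falls on descriptive Part 2 endpoints and possibly on per-protocol membership. Alpha, the stated power and the Part 1 full-analysis-set results are untouched.

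No credible share of patients affected can be given. A reader might divide 12 patients by 5 to 7 sites (1.7 to 2.4 per site) and treat one site's practice as that share of the data. That would assume even recruitment and that every patient at the site starts a drug early. The documents support neither, and Protocol 20.4.3 anticipates 0 to 5 patients per German site.

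That the condition appears more often does not establish which rule the sponsor intends, and this review takes no position on that.

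**What to change.** In both protocol versions:
1. Reconcile 9.5 with 10.11.2 so that one rule covers starting CHI treatments in Part 2, with cross-references from 8.1, 10.2 and 10.11.1.
2. Align 10.2 with 10.11.1 on the medical-monitor discussion for sirolimus and other CHI-specific drugs.
3. State which section governs if wording differs.

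Before database lock, when Protocol 13.3 has the analysis sets fixed, record which departures from the rule count as major deviations and whether a Part 2 departure can remove a patient from the per-protocol set. If conduct is too advanced for an amendment, that record should also say which text was used to classify deviations.

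The content of the rule is for the sponsor's clinicians. The cost is clarification wording. Section 14.8 requires a formal amendment with ethics approval for any protocol change, but no data collection, sample size or primary analysis changes.
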